### 5.5.2 Procedures for discontinuation of a patient from the study

A patient that discontinues will always be asked about the reason(s) for discontinuation and the presence of any AEs. If possible, they will be seen and assessed by an Investigator(s) at 7-day follow-up for the PK Phase and at 4 weeks post-discontinuation for the Continued Supply Phase for the evaluations outlined in [Table 5](#). After discontinuation of study medication, the Principal Investigator (PI)/sub-Investigator will perform the best possible observation(s), test(s) and evaluation(s) as well as give appropriate medication and all possible measures for the safety of the patient. In addition, they will record on the CRF the date of discontinuation, the reasons, manifestation and treatment at the time of discontinuation. If

patients discontinue study treatment, AstraZeneca must be informed immediately. Patients will be required to attend the treatment discontinuation visit. The patient should return all study medication.

After discontinuation of the study medication at any point in the study, all ongoing AEs or SAEs must be followed until resolution unless, in the Investigator's opinion the condition is unlikely to resolve due to the patients underlying disease, or the patient is lost to follow up (see Sections 7.3.3 and 7.3.3.10). All new AEs and SAEs occurring during the 30 calendar days after the last dose of study medication must be reported (if SAEs, they must be reported to AstraZeneca within 24 hours as described in Section 7.3.3.10) and followed to resolution as above. Patients should attend a visit at least 30 days after discontinuing study medication for the collection and/or completion of AE information. Any untoward event occurring subsequent to the 30-day follow-up AE reporting period that the Investigator assesses as possibly related to the study medication should also be reported as an AE.

### **5.5.3 Patient replacement policy**

Replacement of ineligible and non-evaluable patients will be dependent on discussion with AstraZeneca. An evaluable patient is defined as a patient who:

- Met all of the inclusion and exclusion criteria specified in Sections 5.1 and 5.2 within the specified time frame;
- Provided a full PK profile (N.B. if a full PK profile has not been provided then the number of missing PK samples and the corresponding collection time points will be reviewed by AstraZeneca to confirm if the patient is to be replaced);
- Had his/her CRF completed, received and accepted.

[figure not shown]
No patient numbers will be reallocated; any new patients (replacing ineligible or non-evaluable patients) will be enrolled and assigned the next available patient number.

## **6. STUDY CONDUCT**

### **6.1 Patient enrolment and randomisation**

The Principal Investigator will:

1. Obtain signed informed consent from the potential patient before any study specific procedures are performed.
2. Assign potential patient a unique enrolment number, beginning with "E".
3. Determine patient eligibility. See Sections 5.1 and 5.2.

- 
4. Register the screening of a patient by e-mail to the clinical research organisation (CRO) and AstraZeneca, as detailed in the CRF.

If patients have discontinued their participation in the study then they cannot re-enter into the study.

#### **6.1.1 Procedures for randomisation**

Eligible patients will be randomised in a 1:1 ratio (Sequence 1: Sequence 2) for Cohorts 1, 2 and 3 and Group 2 of the Continued Supply Expansion Phase. The actual treatment sequence given to individual patients will be determined by separate randomisation schemes for each cohort.

Eligible patients will be randomised in a 1:1 ratio (Treatment A: Treatment B) for Group 1 of the Continued Supply Expansion Phase.

Eligible patients will be randomised in a 1:1 or 1:1:1 ratio (Treatment A: Treatment B: and Treatment C (if applicable)) for Group 6 of the Continued Supply Expansion Phase.

Eligible patients will be randomised in a 1:1:1:1 ratio (Schedule A: Schedule B: Schedule C: Schedule D) for Group 8, Randomised Tablet Formulation Continued Supply Expansion Phase.

A blocked randomisation will be generated and all centres will use the same list in order to minimise any imbalance in the number of patients assigned to each treatment group. The randomisation scheme will not be stratified for the randomisation of treatment sequences. However, the randomisation of treatment arms for Group 1, 6 and 7 patients in the Continued Supply Expansion Phase will be stratified according to primary tumour type (either breast cancer or ovarian cancer). For Group 6 and 7 both gBRCA breast and gBRCA ovarian patients will be randomised. However, there should be at least 10 gBRCA ovarian patients enrolled per treatment arm; therefore recruitment may be closed to non-ovarian cancer patients before ovarian cancer patients.

Patient eligibility will be established before treatment randomisation. Patients will be randomised strictly consecutively, as patients are eligible for randomisation. Once the eligibility of a patient has been confirmed, the Investigator (or nominated assistant) should contact the Centralised Randomisation Centre by telephone for allocation of randomised treatment sequence or treatment arm and randomisation number. Patients will be identified to the Centralised Randomisation Centre using patient initials, enrolment number and date of birth and which Group the patient is intended to be randomised in to. The Centralised Randomisation Centre will inform the Investigator of the treatment sequence or treatment arm to be allocated to the patient at the randomisation visit.

## 6.2 Treatments

### 6.2.1 Identity of investigational product(s)

AstraZeneca Pharmaceuticals Investigational Products will supply AZD2281, for oral use only, to the Investigator in two presentations. The first presentation is a banded white HPMC size 0 capsule, with a nominal fill weight of 500 mg. The capsules contain a 10% w/w suspension of the drug substance (AZD2281) in a waxy solid (Gelucire 44/14®). The second presentation is green, film-coated tablets containing either 25 mg, 100 mg or 200 mg AZD2281 which will be used in the PK phase and continued supply expansion phase. Tablets are prepared by compression of an amorphous solid dispersion of the drug substance in a carrier polymer prepared by melt extrusion, after blending with common pharmaceutical excipients. AZD2281 will be supplied in white high-density polyethylene (HDPE) bottles with child resistant tamper evident closures.

**Table 8 Identity of Investigational Product**

Investigational product a	Dosage form and strength	Manufacturer	Study Phase
AZD2281 (Gelucire ® 44/14 [capsule] formulation)	50 mg capsule	Patheon Inc	Phase I (PK & Continued supply phase)
AZD2281 (Melt-extrusion [tablet] formulation)	25, 100 & 200 mg tablets	Soliqs	Phase I (PK Phase & continued supply expansion phase)

[figure not shown]
a Descriptive information for AZD2281 Gelucire® 44/14 (capsule) and Melt-extrusion (tablet) formulations can be found in the IB

### 6.2.2 Labelling, storage and accountability

Each bottle will have a label permanently affixed to the outside and will be labelled in accordance with Good Manufacturing Practice and local regulations, stating that the material is for clinical trial/investigational use only and should be kept out of reach of children.

For the Continued Supply Phase, labels will include blank lines for quantity of capsules to be taken, patient enrolment code (E-code) and date of dispensing. Instructions stating that the AZD2281 capsules should be taken at approximately the same time each morning and evening will be included. Following Amendment 4, all labels will instead include the text ‘To be taken as directed by your doctor’, and patients will be provided with specific dosing instructions.

All study medication must be kept in a secure place under appropriate storage conditions and may only be dispensed by a pharmacist or a qualified designee. The investigational product label on the bottle specifies the appropriate storage and shipment. Investigational product should not be stored under refrigerated conditions.

The medication provided for this study is for use only as directed in the protocol. All unused drugs will be accounted for and retained until advised otherwise. The study personnel will account for all drugs dispensed and returned. Certificates of delivery and destruction must be maintained by the study site.

### **6.2.3 Doses and treatment regimens**

#### **6.2.3.1 PK Phase**

Patients will take part in two treatment periods each separated by a 6 to 14-day washout period. Eligible patients will be randomised in a 1:1 ratio (Sequence 1 [Treatment AB]: Sequence 2 [Treatment BA]) for Cohorts 1 and 2. Cohort 3 will be recruited following analysis of PK data from Cohorts 1 and 2. Eligible patients will be randomised in a 1:1 ratio (Sequence 1: Sequence 2).

- Treatment A: Patients will receive a single oral dose of AZD2281 Gelucire® 44/14 (capsule) formulation on Day 1;
- Treatment B: Patients will receive a single oral dose of AZD2281 Melt-Extrusion (tablet) formulation on Day 1.

Cohort 1 will receive a single 50 mg dose of the Gelucire® 44/14 (capsule) formulation and a single 25 mg dose of the Melt-Extrusion (tablet) formulation. Cohort 2 will receive a single 100 mg dose of the Gelucire® 44/14 (capsule) formulation and a single 50 mg dose of the Melt-Extrusion (tablet) formulation. Cohorts 1 and 2 will be recruited consecutively, with Cohort 1 recruited first, immediately followed by Cohort 2. Patients will be randomised to treatment sequence. Cohort 3 will be recruited once PK analysis for Cohorts 1 and 2 has completed so as to be able to better define the higher dose level for the Melt-Extrusion (tablet) formulation in Cohort 3. Patients in Cohort 3 will be randomised to treatment sequence and will receive a single 400 mg dose of the Gelucire® 44/14 (capsule) formulation and a dose of the Melt-Extrusion (tablet) formulation to be decided from the first two cohorts' data. The PK team at AstraZeneca will make the decision about the dose of the Melt-Extrusion (tablet) formulation to be used in Cohort 3, following review of the PK and AUC data from Cohorts 1 and 2 confirming the exposure ratio between the Gelucire® 44/14 (capsule) and Melt-Extrusion (tablet) formulations.

The capsules or tablets should be swallowed whole and not chewed, crushed or divided. Patients will take the study drugs with a total of 240 mL of water, and must consume all the fluid.

#### **6.2.3.2 Continued Supply Phase and Expansion Phase**

##### **Continued Supply Phase**

The Continued Supply Phase is scheduled 7 days after the end of the PK Phase. Gelucire® 44/14 (capsule) formulation AZD2281 will be administered orally at a dose of 400 mg bid (ie, 8 capsules bid) on a continuous basis.

## Continued Supply Expansion Phase

Once the PK team at AstraZeneca have confirmed the exposure ratio between the Gelucire® 44/14 (capsule) and Melt-extrusion (tablet) formulations, approximately 26 additional patients will be recruited to the Continued Supply Expansion Phase: 20 patients with confirmed genetic BRCA1/2 ovarian or breast cancer will be randomised to either daily dosing with tablet or capsule formulation to assess the multiple dose safety profile of the Melt-extrusion (tablet) formulation in a comparative setting and 6 patients will be recruited to Group 2 which will directly compare the steady state PK of the capsule and the Melt-extrusion (tablet) formulation.

Following determination of the AZD2281 plasma concentrations in the samples obtained from the patients in Group 2 of the Continued Supply Expansion Phase, a within-patient comparison of tablet versus capsule steady state AUC and  $C_{max}$  will be performed in order to validate the predictions of steady state exposure previously performed from the single dose data obtained from the patients in the PK Phase. Following this analysis, patients continuing on 200 mg bid AZD2281 tablets may have their daily dose adjusted if required. In addition, further patients will be recruited into the study to assess safety, tolerability and pharmacokinetics of higher doses than 200 mg bid, of the melt-extrusion (tablet) formulation. Initially, a minimum of 6 patients (Group 3) will be treated with 250 mg bid (2 x 100 mg and 2 x 25 mg tablets bid) AZD2281 tablet dose. If tolerated, a further group of 6 patients (minimum) will be recruited to the next Group and will receive increased bid tablet dosing. Dose escalation will continue, into additional groups of 6 patients minimum, at increasing dose levels up to a dose defined by the SRC.

Depending on the determination of tolerability of the tablet dose from Groups 3 onwards, Group 6 patients will either receive:

- 400 mg bid capsule dose, 400 mg bid tablet dose (or lower if 400 mg bid is not tolerated) or a tablet dose between 250mg and the higher tablet dose taken into the expansion that has been shown to be safe and tolerable

OR

[figure not shown]
- 400 mg bid capsule dose or 250 mg bid tablet dose

If 400 mg bid AZD2281 tablet is tolerated and dose escalation continues to a dose defined by the SRC, Group 7 patients will receive:

- 400 mg bid capsule or highest bid tablet dose deemed tolerable by the SRC following completion of the dose escalation phase

Group 8 patients - to further investigate the safety profile and pharmacokinetics of AZD2281 melt-intrusion (tablet) formulation, approximately 60 patients with gBRCA ovarian cancer will be randomised 1:1:1:1 to one of the dosing schedules detailed below:

- 200mg tds tablet continuous dosing

- 
- 250mg tds tablet 2 weeks on study drug, 1 week off study drug
  - 400mg bid tablet 1 week on study drug, 1 week off study drug
  - 400mg od tablet continuous dosing

Patients will continue with their assigned AZD2281 treatment as long as they remain free from intolerable toxicity and, in the Investigator's opinion, are receiving some clinical benefit from treatment with AZD2281 and do not meet any other discontinuation criteria. Following the commencement of continuous treatment of either formulation, study safety assessments will be performed monthly for the first 6 months and then every 8 weeks until treatment discontinuation or study completion (closure of the clinical database - see Section 10.5). If a patient remains on study treatment following the completion of the study (closure of the clinical database), SAEs will continue to be collected until treatment discontinuation.

If the data demonstrate that one treatment arm is significantly more efficacious, then patients who are ongoing on treatment in the less efficacious arm may be permitted to switch to the more efficacious treatment arm following agreement of the investigator and the AZ study physician.

Doses of AZD2281 should be taken at the same times each day, daily (OD) doses should be taken in the morning unless otherwise instructed, twice daily (BD) doses should be taken approximately 12 hours apart and three times (TDS) daily doses taken approximately 8 hours apart. All doses should be taken with approximately 240 mL of water.

Patients will be instructed to take their doses of AZD2281 at least 2 hours after the last time they ate, and the patient should then refrain from eating for a further 2 hours due to the potential effect of food on absorption. For Group 8 patients (excluding Group 8 od schedule patients), and for all other patients (PK phase cohorts 1 and 2, and Groups 1-7) continuing to receive tablet doses following approval of Amendment 4, AZD2281 can be taken with a light meal and the time restrictions on eating will not apply.

For Group 8 od schedule patients an informal assessment of the effect of food on the PK of AZD2281 will be made. On Day 1 these patients must take their dose of AZD2281 at least 2 hours after the last time they ate, and then refrain from eating for a further 2 hours. On Day 8 patients must take their dose of AZD2281 within 30 minutes of eating breakfast. On all other days doses can be taken with a light meal, and no time restrictions are required.

All ongoing patients taking capsule doses of AZD2281 must continue to take their doses of AZD2281 at least 2 hours after the last time they ate, and then refrain from eating for a further 2 hours due to the potential effect of food on absorption of the capsule formulation.

The capsules/tablets should be swallowed whole and not chewed, crushed, dissolved or divided.

If vomiting occurs shortly after the AZD2281 capsules/tablets are swallowed, the dose should only be replaced if all of the intact capsules/tablets can be seen and counted. Should any patient enrolled on the study miss a scheduled dose for whatever reason (eg, as a result of forgetting to take the capsules/tablets or vomiting), the patient will be allowed to take the scheduled dose up to a maximum of 2 hours after that scheduled dose time. If greater than 2 hours after the scheduled dose time, the missed dose is not to be taken and the patient should take their allotted dose at the next scheduled time.

## **6.2.4 Management of toxicity of AZD2281**

### **6.2.4.1 PK Phase**

It is unlikely for patients to experience any toxicities related to a single dose administration of AZD2281. However, dosing must be interrupted if any NCI-CTCAE grade 3 or 4 AE occurs which the Investigator considers to be related to administration of AZD2281. The patient should not enter the second treatment period in their sequence until the toxicity has resolved to at least NCI-CTCAE grade 1. If this has not resolved to at least NCI-CTCAE grade 1 during the maximum 2 weeks (14 days) dose interruption period, the patient must permanently discontinue treatment with AZD2281.

### **6.2.4.2 Continued Supply Phase and Expansion Phase**

Any toxicity observed during the course of the study will be managed by interruption of the dose if deemed appropriate by the Investigator. Repeat dose interruptions are to be allowed as required, for a maximum of 4 weeks (28 days) on each occasion. AZD2281 must be interrupted until the patient recovers completely or the toxicity reverts to NCI-CTCAE version 3.0 grade 1 or less.

Where toxicity recurs following re-challenge with AZD2281, and where further dose interruptions are considered inadequate for management of toxicity, then the patient is to be considered for dose reduction or must permanently discontinue treatment with AZD2281.

Treatment must be interrupted if any NCI-CTCAE grade 3 or 4 AE occurs which the Investigator considers to be related to administration of AZD2281. If this has not resolved to at least NCI-CTCAE grade 1 during the maximum 4 weeks (28 days) dose interruption period, and/or the patient has already undergone the maximum number of dose reductions allowed, the patient must permanently discontinue treatment with AZD2281. If toxicity is appropriately resolved, then the patient should restart treatment with AZD2281 but with a dose reduction according to [Table 9](#) and [Table 10](#). If the event recurs with the same severity, treatment should be interrupted again and, on resolution, a further dose reduction made (see [Table 9](#) and [Table 10](#)). If, on re-starting treatment, the event continues to occur, the patient must permanently discontinue AZD2281.

**Management of new or worsening pulmonary symptoms:** If new or worsening pulmonary symptoms (eg, dyspnoea) or radiological abnormality occurs, an interruption in AZD2281 dosing is recommended and a diagnostic workup (including a high resolution CT scan) should be performed, to exclude pneumonitis. Following investigation, if no evidence of abnormality

is observed on CT imaging and symptoms resolve, then AZD2281 treatment can be restarted, if deemed appropriate by the investigator. If significant pulmonary abnormalities are identified, these need to be discussed with the AstraZeneca Study Delivery Physician.

**Management of leukopaenia and/or anaemia:** An exception to the management of AZD2281-related toxicity is the occurrence of leukopaenia and/or anaemia. In this case, the AE should be managed as deemed appropriate by the investigator (growth factor, transfusions), without interruption in study drug or change in dose. However, growth factors must be discontinued once the AE has recovered to grade 1 or better. They may be resumed, if necessary, if leukopaenia/anaemia develops again and discontinued once it recovers.

**Management of leukopaenia and/or anaemia (Group 8 and ongoing patients):** An exception to the management of AZD2281-related toxicity is the occurrence of leukopaenia and/or anaemia. In this case, the AE should be managed as deemed appropriate by the investigator (e.g. G-CSF or blood transfusions). However, growth factors must be discontinued once the AE has recovered to grade 1 or better. They may be resumed, if necessary, if leukopaenia/anaemia develops again and discontinued once it recovers. In addition:

- Patients who develop a requirement for repeated blood transfusions within 4-6 weeks should be dose reduced.
- Patients who develop grade 3 anaemia should be dose reduced.

**Management of prolonged haematological toxicities including anaemia, neutropaenia or thrombocytopaenia whilst on study treatment:**

- If any study treatment is interrupted/delayed because of one or more of the following:
- ≥2 week interruption/delay in study treatment due to CTC grade >2 neutropaenia
- ≥2 week interruption/delay in study treatment due to CTC grade >2 thrombocytopaenia
- ≥2 week interruption/delay in study treatment due to CTC grade >2 anaemia and or development of blood transfusion dependence

Weekly blood counts should be performed during the study treatment interruption/delay. If the levels have still not recovered to CTC Grade ≤1 after 4 weeks of dose interruption, the patient should be referred to a haematologist for further investigations. Bone marrow analysis or blood cytogenetic analysis should be considered at this stage according to standard haematological practice. Development of myelodysplastic syndrome should be reported as an SAE and full reports must be provided by the Investigator for documentation on the Patient Safety database.

The dose of AZD2281 must not be adjusted under any other circumstances unless AstraZeneca gives prior agreement. Once the dose of AZD2281 has been reduced under no account should it be re-escalated.

AZD2281 should be discontinued for a minimum of 7 days before a patient undergoes therapeutic palliative radiation treatment.

All dose reductions and interruptions, and the reasons for the reductions/interruptions are to be recorded in the CRF.

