#### **6.2.4.3 Dose limiting toxicities**

Dose limiting toxicity (DLT) will be defined as any of the following events that is determined to be possibly or probably related to AZD2281 (as determined by the investigator) and occurring during the first cycle of treatment (28 days), irrespective of whether the toxicity resolved:

- ANC < 0.5 x 10^9/L lasting for > 5 days, or ANC < 0.5x10^9/L with neutropenic fever/sepsis.
- Platelet count < 25 x 10^9/L.
- Any other drug-related non-haematological grade 3/4 toxicity, with the exceptions of fatigue, nausea and vomiting, diarrhoea, myalgia or arthralgia unless appropriate prophylactic or therapeutic measures have been administered.
- Unfavourable tolerability profile compared to 400 mg bid capsule profile used in monotherapy in terms of gastrointestinal toxicities and fatigue (grade 3/4)
- Inability to tolerate the cycle of therapy due to toxicity.
- Grade 2 cardiac or neurological toxicity.
- Any toxicity, which in the judgement of the Sponsor and Investigator is viewed as DLT.

- 
- If any haematological or non-haematological toxicities have not resolved ( $\leq$  Grade 1 CTCAE or baseline levels) within 2 weeks, the patient may be considered to have a DLT and may be discontinued from the trial.

In order to define DLT, patients should not be prophylactically prescribed growth factor support, antiemetics, anti-diarrhoeals or antipyretics during cycle 1 of therapy.

If a patient experiences grade 3 or greater nausea and/or vomiting, diarrhoea, medical intervention should occur, including prophylactic administration of these agents for subsequent doses as indicated.

Patients with dose-limiting toxicity after cycle 2 who have documented clinical benefit (stable disease or an objective response) may continue to be treated at a reduced dose level. Any patient in whom a DLT occurs during any cycle will have his or her treatment held until toxicity resolves to baseline or grade 1 or better. Upon resolution, therapy may be re-instituted at the next lower dose level when clinically indicated. Treatment may be delayed up to 2 weeks to allow sufficient time for recovery from toxicities.

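### Protocol 6.2.4.2 bars interruption or dose change for leukopaenia and anaemia in an unlabelled paragraph that conflicts with the DLT hold and with the paragraph that follows it, and that cuts those patients off from the prolonged-toxicity pathway

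*Protocol*

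**What the plan says.** Section 6.2.4.2 sets a general rule: "Treatment must be interrupted if any NCI-CTCAE grade 3 or 4 AE occurs which the Investigator considers to be related to administration of AZD2281". It allows repeat interruptions "for a maximum of 4 weeks (28 days) on each occasion". It then makes an exception, in two consecutive paragraphs that open with the same sentence: "An exception to the management of AZD2281-related toxicity is the occurrence of leukopaenia and/or anaemia".

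- The first paragraph carries no population label. The event is managed as the investigator sees fit ("growth factor, transfusions), without interruption in study drug or change in dose").
- The second is headed for Group 8 and ongoing patients. It omits the ban on interruption and dose change, and adds that repeated transfusions within 4-6 weeks should lead to a dose reduction, as should grade 3 anaemia: "Patients who develop grade 3 anaemia should be dose reduced". The term ongoing is not defined.

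The same section then describes a pathway for prolonged anaemia, neutropaenia or thrombocytopaenia. Its entry reads "If any study treatment is interrupted/delayed because of one or more of the following", and every listed reason is an interruption or delay of at least 2 weeks. Weekly counts run during the interruption. Referral to a haematologist follows 4 weeks of interruption without recovery to grade 1 or less.

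Section 6.2.4.3 lists as DLTs, among others, ANC below 0.5 x 10^9/L for more than 5 days or with neutropenic fever or sepsis. It states: "Any patient in whom a DLT occurs during any cycle will have his or her treatment held until toxicity resolves". It adds: "Treatment may be delayed up to 2 weeks to allow sufficient time for recovery from toxicities".

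Two other places do not mention the exception. Section 5.5.1 stops treatment in the Continued Supply Phase for grade 3 or 4 events not back to grade 1 or less within 28 days. Table 9 ties dose reductions in Groups 3-7 to related grade 3 or 4 events.

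**The concern.** Section 2.1.4 names bone marrow as the major target organ of toxicity, and anaemia, neutropenia and thrombocytopenia head the clinical findings in Section 2.1.5. Rules on these events are therefore the ones sites will use most.

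Two things are at stake. The first is patient safety: a site cannot obey a ban on interruption and a mandatory hold for the same event, and the enhanced monitoring for persistent cytopenia depends on an interruption that one paragraph forbids. The second is the data: safety is the primary outcome of the expansion phase. If sites resolve the conflict differently, the same blood finding leads to a hold, a reduction or unchanged dosing. Dose intensity, counts of dose reductions and later toxicity would then partly reflect how a site read the text.

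**Working it through.** No sample size, power or event figure is involved, so the check sets the rules side by side by population, trigger and action.

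**1. General rule against the exception.** The mandatory interruption for related grade 3 or 4 events is the rule that both paragraphs openly depart from. That is not a contradiction.

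**2. First paragraph against the DLT hold.** The first paragraph covers leukopaenia and anaemia at any grade and bars interruption. Section 6.2.4.3 requires a hold for any DLT, with no haematological exemption, and the first paragraph does not exempt DLTs. For ANC below 0.5 x 10^9/L meeting the DLT definition, one rule says hold and the other says do not. This assumes that leukopaenia includes neutropaenia, which the mention of growth factor supports. If a site excluded neutropaenia, a conflict could still arise: the last DLT item lets any haematological toxicity unresolved at 2 weeks be considered a DLT, and that could be anaemia.

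**3. First paragraph against Section 5.5.1 and Table 9.** Neither repeats the exception. A grade 3 anaemia lasting more than 28 days is a reason to discontinue under 5.5.1 and, if related, a reason to reduce under Table 9, while the first paragraph bars a change of dose.

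**4. First paragraph against second.** For grade 3 anaemia the first gives no dose change and the second gives dose reduction. They contradict each other for every patient covered by both. If ongoing means everyone still on drug, the first paragraph governs nobody from then on yet remains in force as text. If it means fewer, some patients are denied the change that others must have. The protocol does not settle which.

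**5. Reaching the prolonged-toxicity pathway.**

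- *Patient under the first paragraph:* anaemia or leukopaenia may not cause an interruption, so the 2-week entry condition and the 4-week referral point cannot be met through these events. Reading transfusion dependence as a stand-alone entry does not help, because the weekly counts and the referral are still timed on an interruption.
- *Group 8 or ongoing patient:* interruption is not forbidden, so the pathway opens if the investigator interrupts. The stated action is reduction, which does not open it.
- *Thrombocytopaenia:* outside the exception, so its entry condition works.

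**6. Maximum delay.** Section 6.2.4.3 gives 2 weeks = 14 days. Sections 6.2.4.2 and 5.5.1 give 4 weeks = 28 days, twice as long. Nothing says which governs a haematological DLT. Under the 14-day limit, the referral point at 28 days of interruption is not reached.

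**The case against.** The best defence is that the two paragraphs are sequential. On that reading the first is older text and the second replaces it for Group 8 and for everyone still on treatment. Section 4.1.2.5 starts Group 8 after Group 6 is complete, and the dosing instructions in 6.2.3.2 also distinguish Group 8 from patients continuing on drug. Few or no patients would then remain under the first paragraph. This is plausible, but the protocol does not say it, and the paragraph stands unlabelled in current text.

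A reader might infer that the monitoring pathway is closed to all of Groups 1-7, up to 20 + 6 + 48 + 45 + 30 = 149 patients. The documents do not support that. The sum is an enrolment ceiling, not a count of patients with cytopenia. Any of these patients who count as ongoing fall under the paragraph that permits interruption.

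A reader might also infer that marrow toxicity goes unwatched. It does not. Table 7 schedules haematology on Days 8, 15, 22 and 29 for Groups 3-8 and continues it through Day 169, with visits at least every 8 weeks afterwards. Section 8.1 recommends at least monthly safety bloods. Section 5.5.1 stops treatment at 28 days without recovery. Appendix B gives anaemia requiring transfusion as an example of an event usually considered serious. What is lost is the specific step to weekly counts and referral.

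The 14-day limit can be read as a specific DLT rule over a general one. That is reasonable, but it has to be stated. Finally, the safety summaries are descriptive, with no formal comparison, so no test is distorted. The effect on dose intensity and toxicity counts is possible but unquantified.

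**Conclusion.** The text is wrong as written. The first paragraph conflicts with the DLT hold and is not carved out of the 28-day discontinuation rule or Table 9. It contradicts the second paragraph for any patient covered by both. For a patient managed under it, the anaemia and neutropaenia entries to the prolonged-toxicity pathway are unreachable. For Group 8 and ongoing patients the pathway is reachable, but only by an interruption that the stated action does not call for. The two-fold difference in maximum delay is the weakest part and may need only a sentence.

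The size is conditional. The conflict is complete for whoever falls under the first paragraph, but how many do depends on the undefined word ongoing, and the protocol gives no cytopenia frequency from which to estimate episodes. The conclusion assumes that leukopaenia includes neutropaenia and that both paragraphs are in force.

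**What to change.** 1. State which patients each of the two leukopaenia and anaemia paragraphs in 6.2.4.2 covers, and define ongoing patients. If the sponsor confirms that the first paragraph is superseded, delete it.
2. Reconcile Sections 5.5.1, 6.2.4.2 (with Table 9) and 6.2.4.3 so that each group has one consistent instruction on hold, dose reduction and maximum delay, including for a haematological DLT.
3. Reconcile the entry condition of the prolonged-toxicity pathway with those instructions, and state whether its weekly counts and referral apply to patients whose dosing was not interrupted.

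The clinical rule in each case is for the sponsor's physicians to choose. The cost is protocol wording in the next amendment and a notice to sites. Any added monitoring would follow from what the physicians decide under item 3.
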